6.1 Study Objectives

The objective of this first-in-human study is to assess the safety and feasibility of electroporation/PEF as a technology to achieve selective GP ablation.

The primary hypothesis is that selective GP ablation (i.e. with minimal myocardial ablation) will lead to an extension in the atrial effective refractory period.

6.2 Study Design

This is a prospective, single arm, exploratory study of safety and feasibility in the treatment of up to 30 patients undergoing cardiothoracic surgery; as such no control or comparator group is required. The study will be performed at two sites;

- Tbilisi Heart & Vascular Clinic, Tbilisi, Georgia.
- Na Homolce Hospital, Prague, Czech Republic.

The primary feasibility endpoint will be demonstration of ability to access and deliver Pulsed Electric Field energy to all of the targeted ablation sites.

A primary efficacy end point will be to achieve an extension in the atrial effective refractory period (AERP) through the Pulsed Electric Field ablation of the GPs. Experimental and clinical data indicates that GP ablation extends AERPs.

A secondary efficacy endpoint will be the incidence of post-operative atrial fibrillation up to the point of patient discharge. Ablation of GPs is a potential prophylactic treatment for post-operative atrial fibrillation. Data will be collected to quantify duration (from ICU arrival) to first incidence of POAF, duration of first POAF episode and standard of care method used to treat the POAF. POAF is defined as any AF of 30 seconds or longer duration.

This exploratory treatment will be performed on patients undergoing elective open-chest cardiothoracic surgery. Once the heart is exposed, the treatment is performed before the elected procedure; the exploratory treatment and measurements will take 35-40 minutes to complete.

The sponsor will supply the ablation catheters, the pulsed electric field generator, the ECG synchronization unit and the patient dispersive pad. The investigation site will be expected to supply the stimulator and recording system for measurement of AERP, including the necessary temporary epicardial pacing wires. In addition, a conventional irrigation pump and tube set is required on-site for delivery of physiological saline through the ablation catheter during the pulse delivery.

6.3 Study Rationale

This study is intended to evaluate the safety and feasibility of the OCED system to ablate autonomic ganglionated plexi structures on the epicardial surface of the heart. The patient population will be those undergoing coronary artery bypass grafting (CABG).

6.4 Sample size

The study will include up to 30 patients with completed GP ablations. The justification for the number of test subjects is described in the **Statistical Justification** section below.

A subject is considered enrolled once he/she signs the informed consent form. All enrolled subjects will then proceed to complete the screening and any applicable baseline tests. If they do not meet the study criteria they will be withdrawn from the study and will not count towards the treated study population. If a subject meets all inclusion criteria and none of the exclusion criteria and are deemed eligible for this study, they will be treated with the study device and system. Patients will be followed for approximately 12 months post-procedure.

6.5 Statistical Justification and Analysis of Results

This trial is intended to demonstrate safety and feasibility and is not designed to be a statistically significant study. As a result, no formal statistical hypothesis is planned to derive the appropriate sample size.

For all primary safety and performance endpoints, the 95% 2-sided exact binomial confidence intervals will be presented.

For the secondary end-point of AERP extension, it is anticipated that a 10% extension may be obtained. This will be assessed using Paired t-testing from the pre-treatment and post-treatment AERP values from all patients.

6.6 Site Selection and Training

All operators included in this clinical trial will be trained by the Sponsor in the use of investigational device. Study training will be documented and will include a review of the following:

- the investigational plan,
- ISO 14155, Declaration of Helsinki (2013),
- SAE reporting,
- Good Clinical Practices (GCPs)
- and all study procedures.

Each site will have a site qualification visit to assure the Investigator clearly understands and accepts the obligations incurred in undertaking the study and that the facilities and systems for conducting the study are acceptable. Each site must have equipment for conducting cardiac ablation procedures including equipment for cardiac pacing and recording and should have permission according to local law to perform cardiac ablations.

6.7 Patient Inclusion Criteria

- Age is between 18 and 70 years.
- Scheduled for open-chest cardiothoracic surgery, for coronary artery bypass grafting.
- Legally competent and willing to sign the informed consent.
- Life expectancy of at least 2 years.

DESCRIPTION: CIP-001 Clinical Investigation Plan for OCED System

6.8 Patient Exclusion Criteria

A potential subject who meets any of the following criteria will be excluded from participation in this study:

- Previous cardiac surgery.
- Prior pericardial interventions.
- Prior pulmonary vein isolation (PVI).
- Previous or existing pericarditis.
- Persistent or long-standing persistent atrial fibrillation.
- Indication for surgical ablation or PVI for atrial fibrillation.
- Indication for concomitant surgical valve repair or replacement.
- Indication for concomitant left atrial appendage (LAA) ligation or excision.
- History of previous radiation therapy on the thorax.
- History of previous thoracotomy.
- Prior electrical or mechanical isolation of the Left Atrial Appendage (LAA).
- The presence of LAA occlusion devices, coronary stents, prosthetic heart valves, pacemakers or implantable cardioverter defibrillators (ICDs).
- Myocardial infarction within the previous 2 months.
- NYHA Class IV heart failure symptoms.
- Left ventricular ejection fraction (LVEF) < 40%, measured by transthoracic echocardiography (TTE).
- Left atrial (LA) diameter > 5.0 cm, measured by transthoracic echocardiography (TTE).
- The presence of left atrial thrombus when examined by transoesophageal echocardiography (TEE).
- The presence of AF attributable to non-cardiovascular causes such as thyroid disease, electrolyte imbalance/dehydration or other reversible causes.
- Active infection or sepsis as evidenced by increased white blood cell count, elevated CRP or temperature > 38.5°C.
- Known or documented carotid stenosis > 80%
- Stroke or transient ischemic attack within the previous 6 months.
- Known or documented epilepsy.
- Pregnancy or child-bearing potential without adequate contraception.
- Circumstances that prevent follow-ups.
- Drug abuse.
- Patients cannot be enrolled in another clinical study

The study will involve up to 30 patients with completed GP ablations. Recruitment is anticipated to be completed within 9 months.

Subjects may withdraw from the study at any time for any reason if they wish to do so without any consequences. The investigator can decide to withdraw a subject from the study for urgent medical reasons. Patient recruitment will be terminated prematurely at any time if the risk of serious adverse events exceeds the expected benefit of the trial.

7. Study Endpoints

7.1 Primary Safety Endpoint:

Rate of device related Primary Safety Adverse Events within 30 days of the procedure. Primary Safety Adverse Events include:

- 1. Atrial perforation or excessive bleeding (excessive bleeding is defined as bleeding which requires any blood transfusion).
- 2. Pericarditis
- 3. Pericardial effusion
- 4. Cardiac tamponade (if either surgical or percutaneous drainage is required).
- 5. Constrictive pericarditis, requiring re-operation.
- 6. Newly developed sinus node dysfunction.
- 7. Newly developed first, second or third degree atrioventricular (AV) block
- 8. Vasovagal reactions during hospital stay
- 9. Ventricular fibrillation

7.2 Primary Feasibility Endpoints:

The primary feasibility endpoint includes confirmation of access and delivery of Pulsed Electric Field energy to targeted ablation sites.

7.3 Efficacy Endpoints:

The clinical effectiveness endpoints are defined as the following:

- A primary efficacy end point will be confirmation of an extension in the atrial effective refractory period (AERP) through the Pulsed Electric Field ablation of the GPs. Experimental and clinical data indicates that GP ablation extends AERPs.
- A secondary efficacy endpoint will be the incidence of post-operative atrial fibrillation up to the point of patient discharge. Ablation of GPs is a potential prophylactic treatment for post-operative atrial fibrillation. Data will be collected to quantify duration (from intensive care unit (ICU) arrival) to first incidence of POAF, duration of first POAF episode and standard of care method used to treat the POAF. POAF is defined as any AF of 30 seconds or longer duration³³.

8. Study Procedure and Data Collection

The following baseline data must be collected prior to the procedure for all subjects meeting the inclusion criteria (*Assumed to be standard of care):

- Baseline:
 - Inclusion/Exclusion criteria
 - Signed Informed Consent
 - Frequency of reported episodes of atrial fibrillation *
 - Medical History including NYHA class *
 - Documentation of Smoking and Substance abuse *
 - Medication History, review of current and past Medications*
 - General Physical Exam*
 - 12 Lead ECG*
 - 24Hr Holter recording documentation of AF, frequency and severity of AF and presence of asymptomatic episodes if relevant
 - TTE for LVEF and LA diameter*
 - Blood sample for laboratory investigation comprising Hgb, WBC, Platelet, Na, K, Creatinine, NTproBnP, Troponin, C-reactive protein, TSH, INR *
 - Short form-36 (SF-36) QOL
 - TEE to assess for LA thrombus per elective procedure*

The procedures required for screening and baseline may be conducted during more than one visit, provided that all procedures are conducted within 90 days prior to the index procedure.

- ¹²³I-*m*IBG Scintigraphy and SPECT UMC Amsterdam only
- Study Procedure:

After opening of the chest (and after cannulation at the discretion of the operator), but before cardiopulmonary bypass and cardioplegia, baseline atrial effective refractory period (AERP) will be determined. The atrial GPs will then be ablated, with AERP measurements performed at intermediate timepoints and after all GP ablations.

Paralytic Agent

In addition to standard of care general anaesthesia, a paralytic agent or nerve block needs to be administered to suppress skeletal muscle stimulation. Vecuronium or Rocuronium are the preferred drug options as these have minimal impact on AERP values; however, the baseline AERP reading should be taken with paralytic already administered, just before the first ablation.

Measurement of AERP

AERP will be measured at any one, or more, of the following sites: left atrial appendage, left atrium or right atrium, depending on clinician preference. Measurements will be performed using temporary epicardial pacing wires; one wire connected to the measurement site (-ve) and one wire positioned subcutaneously (+ve); the wires are connected to the stimulator unit of an EP system. A standard diagnostic quadripolar EP catheter will be positioned behind the atrium and connected to the EP system for recording atrial activation and sensing of capture. Check that the temperature of the heart is 36°C -1/+2°C just before, during or just after AERP measurement.

AERP will be determined with standard premature pacing protocols. Pace the measurement site (i.e. left atrial appendage, left atrium or right atrium) with a train of 8 S1 cycles at Basic Cycle Length 500 ms, output

in range 10-20 mA, pulse width 2-3 ms, followed by an S2 of 400 ms. Once capture of S2 is confirmed immediately continue with the next pacing train. Progressively shorten S2 by 50 ms per cycle, until loss of capture is observed. Then retry at the last S2 coupling interval that captured and reduce coupling interval of S2 by 10 ms per cycle until loss of capture is observed on 2 consecutive occasions. The longest S2 coupling interval that does not capture is the AERP.

If attempts to measure AERP result in atrial fibrillation or atrial flutter, a cardioversion should be attempted, after which a waiting time of 10 minutes is needed before new attempts to measure AERP are undertaken. If more than one cardioversion is needed, removing that patient from the study analysis should be considered.

Ablation of GPs

The GPs to be ablated in this study are illustrated in Figure 4. The sequence of the ablations will be as follows:

1) Oblique Sinus GP (OSGP)

These are the retro-atrial GPs located on the posterior left atrium, close to the junction of the pulmonary veins and the left atrium. They are sometimes separately identified as the inferior left GP (ILGP) and inferior right GP (IRGP).

- Right Superior GP (RSGP)
 This is located on the anterosuperior surface of the right atrium, medial to the superior vena cava/right atrium junction and lateral to the aortic root.
- Transverse Sinus GP (TSGP)
 This is located at the base of the aorta and pulmonary artery within the transverse sinus.
- Left Superior GP (LSGP)
 The superior left GP is located at the junction of the left superior pulmonary vein with the posterior left atrium, in the left superolateral area.
- Ligament of Marshall GP (LMGP)
 This is located between the anterior aspect of the left pulmonary veins and the posterior left atrial appendage.

[figure not shown]

Figure 4: Targeted ablation locations; OSGP, RSGP, TSGP, LSGP and LMGP.

AERP will be determined at baseline (before ablations) and after all ablations are completed. In addition, at the discretion of the operator, intermediate AERP measurements may be made after ablation of the OSGP and after TSGP ablation. The sequence of ablations and measurements is therefore as shown in Figure 5. The OSGP is ablated with the Glove catheter while all other sites are ablated with the Finger catheter. Each ablation sequence consists of 10 sequential ECG-gated pulses; each pulse at 1000 V and of 100 μs duration. Each GP location is ablated with between three and six of these sequences; in some instances a pull-back of a few millimetres or catheter repositioning is allowable between sequences in order to ensure good coverage of the target area. Optionally, the OSGP may be treated using separate approaches from the left and right sides i.e. individually treating the inferior left and inferior right GPs with up to three sequences each, rather than treating them as a single entity. A 0.9% normal saline solution is irrigated through the catheter at a flow rate of 2 ml/min, during ablation only.

[figure not shown]

Figure 5: Sequence of ablations and AERP measurements

Document electrical cardioversion or defibrillation during the procedure in the study records. The record should indicate when this was performed i.e. before ablations/measurements, between specific ablations/measurements or after final AERP measurement (during the index procedure).

DESCRIPTION: CIP-001 Clinical Investigation Plan for OCED System

Rev: H

Index Cardiac Surgery Procedure

Upon completion of GP ablations and AERP measurements, the elected cardiothoracic surgery will progress as planned.

- Post-Operative Care and Discharge:
 - Adverse Events and Concomitant AAD-ATT Medication
 - Cardiac telemetry through to discharge.
 - o ECG
 - Physical Exam
- Follow-Up at 30 Days:
 - o 24 Hr. Holter for Frequency and Duration of atrial arrhythmias
 - Adverse Events and Concomitant AAD-ATT Medication
 - o ECG
 - Physical Exam
- 3 months:

•

- o 24 Hr. Holter for Frequency and Duration of atrial arrhythmias
- Adverse Events and Concomitant AAD-ATT Medication
- o ECG
- Physical Exam
- 6 months:
 - 24 Hr. Holter for Frequency and Duration of atrial arrhythmias
 - Adverse Events and Concomitant AAD-ATT Medication
 - o ECG
 - Physical Exam
 - Blood sample for laboratory investigation comprising Hgb, WBC, Platelet, Na, K, Creatinine, NTproBnP, Troponin, C-reactive protein, TSH, INR
- 12 months:
 - 24 Hr. Holter for Frequency and Duration of atrial arrhythmias
 - Short Form-36 (SF-36) QOL
 - Adverse Events and Concomitant AAD-ATT Medication
 - o ECG
 - Physical Exam
 - o NYHA score

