discerned whether these effects are caused by GP ablation or by more atrial myocardial ablation, resulting in more rigorous and longer lasting PVI. The AFACT trial attempted to overcome these issues by randomizing patients undergoing thoracoscopic ablation of AF between additional epicardial radiofrequency ablation of the 4 major GPs versus no additional GP ablation. The study showed no benefit in absence of AF after one and two years, but significantly more surgical complications, mainly major bleedings²³. Also, more sinus node dysfunction was noted in the GP group, and more pacemaker implantations. A sub-analysis of recurrences in AFACT showed that atrial tachycardias were more frequently noted in the GP ablation group, at least suggesting that the myocardial substrate was modified by GP ablation to facilitate atrial tachycardias. Therefore, it is very well possible that epicardial radiofrequency GP ablation in AFACT was not tissue selective, and additional myocardial ablation took place, resulting in the adverse effect of more atrial tachycardias.

Hence, radiofrequency ablation appears not selective for the GPs, and inadvertent myocardial ablation seems to occur both with endocardial as with epicardial approaches. An ablation approach selective for nervous system tissue may overcome this and may combine the potential benefits of GP ablation with the absence of iatrogenic atrial tachycardias.

Electroporation to cause selective irreversible cell damage within the GP - with minimum myocardium ablation.

Electroporation refers to the principle that cell membranes become permeable when subjected to high voltage, which results in apoptosis and cell death. Typically, very short episodes (microseconds) of high voltage are applied to the tissue to ablate. This technology has been used successfully in the treatment of various types of cancer^{24,25}. One of the attractive features of the technology is the relative tissue selectivity, allowing ablation of the tissue of choice while sparing the surrounding structures, such as for example vessels²⁶ Particularly larger cells, such as neurons appear vulnerable for electroporation^{27,28}. Therefore, in this instance, the electroporation enables irreversible damage to the GP, while sparing the myocardium and other adjacent tissues.

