The Investigator will document all Serious Adverse Events (SAE) and Serious Adverse Device Effects (SADE), including device deficiencies in the study participant's patient file and report it to the Sponsor, within 24-hours of knowledge of event.

In categorising the adverse event and observed device deficiency the principal investigator shall refer to ISO 14155 Annex F- Adverse event categorization. The investigator will document the action taken in relation to the investigational device and to other treatments.

The Investigator will also report to the EC, without unjustified delay, all serious adverse events and device deficiencies that could have led to a serious adverse device effect. This information shall be promptly followed by detailed written reports. The Investigator must notify the sponsor once the EC has been notified.

The principal investigator shall supply the sponsor, upon sponsor's request, with any additional information related to the safety reporting of a particular event. Source data are preferentially immediately transferred to the ADVERSE EVENT CRF. When medical reports (lab results, examinations, etc.) associated with adverse events are submitted to the CRO or sponsor, all personal subject

information (name, address, etc.) MUST be removed or redacted. The redacted materials must be identified only with the Site and subject's study numbers.

The investigator will monitor all AEs until they are resolved, determined to be a chronic condition or the subject is lost to follow-up. The investigator will report all AEs regardless of whether they are anticipated or unanticipated and regardless of classification, seriousness, severity, outcome or causality.

Assessment of Adverse Event Severity:

Where the determination of AE severity rests on medical judgment, the determination of severity must be made with the appropriate involvement of a medically qualified investigator.

The severity of AEs will be graded using the following definitions:

Mild awareness of sign, symptom, or event, but easily tolerated

Moderate:discomfort enough to cause interference with usual activity and may warrant interventionSevere:incapacitating with inability to do usual activities or significantly affects clinical status and
warrants intervention.

Relationship to the Device and related procedure:

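### Patients with existing sinus node dysfunction or AV block may be treated, but the primary safety rate counts only new disease, so device-related worsening of sinus node dysfunction, even to a pacemaker, is left out

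*Combined protocol and SAP*

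**What the plan says.** **Eligibility.** The four inclusion criteria in section 6.7 cover age, planned surgery ("Scheduled for open-chest cardiothoracic surgery, for coronary artery bypass grafting"), consent and life expectancy. None concerns rhythm or conduction. Among the 26 exclusions in section 6.8 and the synopsis, the only one bearing on conduction disease is a device already in place: "The presence of LAA occlusion devices, coronary stents, prosthetic heart valves, pacemakers or implantable cardioverter defibrillators (ICDs". Sinus node dysfunction, AV block and bradycardia are not mentioned. Section 6.4 states that subjects who meet the criteria and are deemed eligible are treated.

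**Primary safety endpoint (section 7.1).** The measure is "Rate of device related Primary Safety Adverse Events within 30 days of the procedure". Nine components are listed. Item 6 is "Newly developed sinus node dysfunction" and item 7 is "Newly developed first, second or third degree atrioventricular (AV) block". The plan gives no definition of newly developed and no criterion for sinus node dysfunction. Pacemaker implantation is not on the list.

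**Known hazard (section 1).** Of an earlier randomised trial of epicardial radiofrequency GP ablation, the background reports: "Also, more sinus node dysfunction was noted in the GP group, and more pacemaker implantations".

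**Other safety capture (section 8.8).** "The investigator will report all AEs regardless of whether they are anticipated or unanticipated and regardless of classification, seriousness, severity, outcome or causality".

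**Baseline data (section 8).** Medical history, a 12-lead ECG and a 24-hour Holter are collected. The Holter is described in terms of AF only: "24Hr Holter recording documentation of AF, frequency and severity of AF and presence of asymptomatic episodes if relevant".

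**The concern.** The entry rule and the endpoint rule do not fit together. Patients with existing conduction disease may enter, but two of the nine components are written as if nobody had such disease at entry. Sinus node dysfunction is the firmer problem, because item 6 has no grades: someone who already has the condition cannot newly develop it. If that patient deteriorates after ablation and receives a pacemaker, neither the deterioration nor the pacemaker is a component.

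This matters because the study is first-in-human and its headline safety output is one rate with an exact interval (section 6.5). The background names sinus node dysfunction and pacemaker implantation as harms seen with earlier GP ablation. One of these is absent from the endpoint and the other is limited to undefined new cases. Any resulting error makes the rate look better, never worse.

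**Working it through.** The documents state no figure on this point, so there is nothing to reproduce. The check is a reading of the rules followed by an illustration.

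**Step 1: apply sections 6.8 and 7.1 to three hypothetical patients.** None has a pacemaker or ICD at entry. In each, the event is device related, falls within 30 days, and is the only event.

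| Baseline | Event after ablation | Excluded by 6.8? | Counted by 7.1? |
|---|---|---|---|
| No conduction disease | Sinus node dysfunction | No | Yes, item 6 |
| Sinus node dysfunction | Worsens; pacemaker implanted | No | No: not new, and a pacemaker is not a component |
| First-degree AV block | Third-degree AV block | No | Unclear: yes if each degree is a separate event, no if AV block is one condition |

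The second row is the gap. The third is an ambiguity.

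**Step 2: effect on the primary rate.** Inputs: at most 30 treated patients (section 6.4) and two-sided 95% exact binomial intervals (section 6.5). I assume that all 30 are treated and analysed. For x events in n patients the Clopper-Pearson limits are

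- lower = Beta quantile(0.025; x, n − x + 1), or 0 if x = 0
- upper = Beta quantile(0.975; x + 1, n − x)

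For x = 0 the upper limit reduces to 1 − 0.025^(1/n).

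- 0/30: upper limit = 1 − 0.025^(1/30) = 11.6%
- 1/30 = 3.3%: 0.1% to 17.2%
- 2/30 = 6.7%: 0.8% to 22.1%

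One uncounted worsening, with no other event in the study, is reported as the first line when the second is true.

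**Step 3: could such a patient be enrolled?** The documents give no prevalence. For an assumed prevalence p, the chance that at least one of 30 has existing disease is 1 − (1 − p)^30:

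| Assumed p | Chance of at least one in 30 |
|---|---|
| 2% | 45% |
| 5% | 79% |
| 10% | 96% |
| 20% | 99.9% |

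This is the chance that the gap is open, not that an event is missed. A missed event also needs worsening within 30 days, a device-related judgement, and no other listed event in that patient.

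**Step 4: component rates.** With 1, 3 or 6 of 30 patients (assumed) already having the condition, 29, 27 or 24 can develop it anew. With zero events the upper limits are 1 − 0.025^(1/29) = 11.9%, 1 − 0.025^(1/27) = 12.8% and 1 − 0.025^(1/24) = 14.2%, against 11.6% for 30. These denominators suit a rate for item 6 or item 7 alone. They do not suit the nine-item composite, because a patient with existing sinus node dysfunction is still at risk for the other eight items.

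**The case against.** **Worsening is not lost to the study.** Section 8.8 requires every AE to be reported whatever its class or causality, with relatedness assessed. A pacemaker implanted to prevent life-threatening illness or permanent impairment falls under the SAE definition and goes to the sponsor within 24 hours. Telemetry runs to discharge, and ECGs are taken at discharge and at each follow-up visit. This stands: a reader might infer that the study is blind to worsening, and the documents do not support that. What remains is that an AE listing does not correct the headline rate. The Clinical Events Committee is no substitute, because it reviews only events in question (section 13.9).

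**AV block progression may already count.** Item 7 names each degree, so a move from first to third degree can be read as a new third-degree block. This stands, and it is why the firm gap is limited to sinus node dysfunction.

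**The risk premise is thin.** A reader might infer that patients with existing disease are the most exposed to harm, or carry avoidable risk. The background does not say so. It reports more sinus node dysfunction and pacemakers in the GP group overall, with no breakdown by baseline conduction status and no mention of AV block. It also concerns radiofrequency energy in thoracoscopic AF surgery, not pulsed electric field in CABG patients. This stands.

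**New events are easier to attribute.** In a single-arm study alongside CABG, worsening of existing disease may be natural history, which section 8.8 says must be considered. That is a fair reason for the present wording. But the endpoint already requires device-relatedness, and that requirement would apply to worsening as well.

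**No decision turns on the number.** The study is descriptive, with no safety threshold. This is true and limits the severity, but the rate and its interval are what will be reported.

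**Conclusion.** The point holds in a limited form. Followed as written, sections 6.8 and 7.1 allow a device-related worsening of existing sinus node dysfunction, including one that leads to a pacemaker, to add nothing to the primary safety rate while the patient stays in the denominator. For AV block the text is ambiguous rather than wrong.

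The loss is conditional. It requires that such a patient is enrolled and worsens within 30 days, that the event is judged device related, and that no other component occurs. It is therefore too strong to say that the rate is biased downward as a matter of fact; it can be, and only in that direction. For one such event the reported result would be 0/30 in place of 1/30, with the upper 95% limit at 11.6% in place of 17.2%. How likely this is cannot be derived from the documents.

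Nor do the documents settle whether these patients should be excluded. A reader might infer that they should, but that is a clinical judgement for the sponsor. The statistical point is that the two sections must be reconciled. It is a cheap improvement worth making.

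**What to change.** 1. In section 7.1 and the synopsis, change items 6 and 7 to cover disease that is *newly developed or worsened from baseline*, judged against the baseline ECG, Holter and history. State that a higher degree of AV block or a new pacemaker counts as worsening. Keep the device-related requirement and the 30-day window.
2. State the criterion used for sinus node dysfunction, so that new and worsened can be applied in the same way at both sites. Have the Holter reading record conduction findings as well as AF.
3. Report the two component rates, with exact intervals, among all treated patients and among those free of the condition at baseline. Keep all treated patients as the denominator of the composite.
4. Carry the same wording into section 8.9, which repeats the newly developed phrasing.
5. Reconcile section 6.8 with section 7.1 by an explicit statement on existing conduction disease. Whether eligibility changes is for the sponsor to decide.

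The cost is mainly wording, since the history, ECG and Holter are already collected. The rate may look slightly less favourable, and worsening is harder to attribute than new disease; the device-related requirement is the safeguard for that.
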